11.0 MEASUREMENT OF EFFECT

Response and progression will be evaluated in this study using the new international criteria proposed by the revised Response Evaluation Criteria in Solid Tumors (RECIST) guidelines (version 1.1).

Changes in the largest diameter (unidimensional measurement) of the tumor lesions and the short axis measurements in the case of lymph nodes are used in the RECIST guideline [38].

11.1 Schedule of Evaluations

For the purposes of this study, patients should be reevaluated every 12 weeks (+/- 1 week).

Supporting documentation of response should be submitted per Section 6.1.1, and radiologic images and local interpretation reports should be submitted per Section 6.3.

11.2 Definitions of Measurable and Non-Measurable Disease

11.2.1 Measurable Disease

A non-nodal lesion is considered measurable if its longest diameter can be accurately measured as ≥ 2.0 cm with chest x-ray, or as ≥ 1.0 cm with CT scan or MRI.

A superficial non-nodal lesion is measurable if its longest diameter is ≥ 1.0 cm in diameter as assessed using calipers (e.g. skin nodules) on imaging. In the case of skin lesions, documentation by color photography, including a ruler to estimate the size of the lesion, is recommended.

A malignant lymph node is considered measurable if its short axis is >1.5 cm when assessed by CT scan (CT scan slice thickness recommended to be no greater than 5 mm).

Tumor lesions in a previously irradiated area are considered measurable disease if there has been evidence of disease progression in the previously irradiated area in the 6 months prior to registration.

11.2.2 Non-measurable Disease

Non-measurable disease includes disease smaller than these dimensions or lesions considered truly non-measurable including: leptomeningeal disease, ascites, pleural or pericardial effusion, lymphangitic involvement of skin or lung.

11.3 Guidelines for Evaluation of Measurable Disease

11.3.1 Measurement Methods

All measurements should be recorded in metric notation (i.e. decimal fractions of centimeters) using a ruler or calipers.

The same method of assessment and the same technique must be used to characterize each identified and reported lesion at baseline and during restaging. For patients having only lesions measuring at least 1 cm to less than 2 cm must use CT imaging for both pre- and post-treatment tumor assessments.

Imaging-based evaluation is preferred to evaluation by clinical examination when both methods have been used at the same evaluation to assess the antitumor effect of a treatment.

11.3.2 Acceptable Modalities for Measurable Disease

• Conventional CT and MRI: This guideline has defined measurability of lesions on CT scan based on the assumption that CT slice thickness is 5 mm or less.

- O As with CT, if an MRI is performed, the technical specifications of the scanning sequences used should be optimized for the evaluation of the type and site of disease. The lesions should be measured on the same pulse sequence. Ideally, the same type of scanner should be used and the image acquisition protocol should be followed as closely as possible to prior scans. Body scans should be performed with breath-hold scanning techniques, if possible.
- Chest X-ray: Lesions on chest x-ray are acceptable as measurable lesions when they are clearly defined and surrounded by aerated lung. However, CT scans are preferable.

11.3.3 Measurement at Follow-up Evaluation

The cytological confirmation of the neoplastic origin of any effusion that appears or worsens during treatment when the measurable tumor has met criteria for response or stable disease is mandatory to differentiate between response or stable disease (an effusion may be a side effect of the treatment) and progressive disease.

Cytologic and histologic techniques can be used to differentiate between PR and CR in rare cases (e.g. residual lesions in tumor types such as germ cell tumors, where known residual benign tumors can remain.)

11.4 Measurement of Treatment/Intervention Effect

11.4.1 Target Lesions & Target Lymph Nodes

Measurable lesions (as defined in Section 11.2.1) up to a maximum of 5 lesions, representative of all involved organs, should be identified as "Target Lesions" and recorded and measured at baseline. These lesions can be non-nodal or nodal (as defined in Section 11.2.1), where no more than 2 lesions are from the same organ and no more than 2 malignant nodal lesions are selected.

Note: If fewer than 5 target lesions and target lymph nodes are identified (as there often will be), there is no reason to perform additional studies beyond those specified in the protocol to discover new lesions.

Target lesions and target lymph nodes should be selected on the basis of their size, be representative of all involved sites of disease, but in addition should be those that lend themselves to reproducible repeated measurements. It may be the case that, on occasion, the largest lesion (or malignant lymph node) does not lend itself to reproducible measurements in which circumstance the next largest lesion (or malignant lymph node) which can be measured reproducibly should be selected.

Baseline Sum of Dimensions (BSD): A sum of the longest diameter for all target lesions plus the sum of the short axis of all the target lymph nodes will be calculated and reported as the baseline sum of dimensions (BSD). The BSD will be used as reference to further characterize any objective tumor response in the measurable dimension of the disease.

Post-Baseline Sum of the Dimensions (PBSD): A sum of the longest diameter for all target lesions plus the sum of the short axis of all the target lymph nodes will be calculated and reported as the post-baseline sum of dimensions (PBSD). If the radiologist is able to provide an actual measure for the target lesion (or target lymph node), that should be recorded, even if it is below 0.5 cm. If the target lesion (or target lymph node) is believed to be present and is faintly seen but too small to measure, a default value of 0.5 cm should

be assigned. If it is the opinion of the radiologist that the target lesion or target lymph node has likely disappeared, the measurement should be recorded as 0 cm.

The minimum sum of the dimensions (MSD) is the minimum of the BSD and the PBSD.

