7.2.3 Retrospective Imaging Central Review

To ensure the highest standards and consistency, the following complete CT or MRI (and CXR or non-contrast CT) imaging data sets will be collected and submitted for quality checks and retrospective centralized primary endpoint assessment image reviews by the A021602 Imaging Central Review Panel:

- Baseline scan
- Restaging scans with local determination of CR, PR, or SD during blinded therapy

The centralized image reviews by the A021602 Imaging Central Review Panel will be performed every 6 months for each patient starting from the date of patient registration until the date of centrally-confirmed radiographic disease progression or start of new anticancer therapy, whichever comes first. At minimum, the central reviewer will assess

the scans from the two time points within the 6-month period, however, scans from any previous periods may also be reviewed if desired by the central reviewer to ensure an accurate interpretation. Scans will be reviewed in batches every quarter for any patients who have reached the 6-month benchmark within the preceding three calendar months.

IROC Ohio will contact the A021602 Imaging Central Review Panel 3 days ahead (except weekends and holidays) for scheduling the batched centralized image reviews. Reviewers' availabilities should be sent (at least quarterly) to IROC Ohio in advance for this purpose. The batched centralized image reviews will be performed using an IROC Ohio established thin-client remote review approach.

In the event there is disagreement between central reviewers with previously recorded central review measurements, a blinded adjudication by another central reviewer will occur; the adjudicator will not be the same radiologist that performed either of the central reviews in question. The adjudicator's decision will be used as the retrospective, batched central review decision for the purposes of the primary study endpoint.

Results of the batched centralized image reviews will not be reported back to the site PI.

There will be no comparison between the real-time image central review results and the retrospective image central review results.

The A021602 Imaging Central Review Panel will initially consist of the University of California, San Francisco and University; other qualified radiologists may be added to the panel in the future upon approval by IROC Ohio, the Alliance, and the Study Chair.

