11.4.3 Response Criteria

All target lesions and target lymph nodes followed by CT/MRI/Chest X-ray must be measured on re-evaluation at evaluation times specified in Section 11.1. Specifically, a change in objective status to either a PR or CR cannot be done without re-measuring target lesions and target lymph nodes.

Note: Non-target lesions and non-target lymph nodes should be evaluated at each assessment, especially in the case of first response or confirmation of response. In selected circumstances, certain non-target organs may be evaluated less frequently. For example, bone scans may need to be repeated only when complete response is identified in target disease or when progression in bone is suspected.

- Evaluation of Target Lesions
 - o Complete Response (CR): All of the following must be true:
 - Disappearance of all target lesions.
 - Each target lymph node must have reduction in short axis to < 1.0 cm.
 - Partial Response (PR): At least a 30% decrease in PBSD (sum of the longest diameter for all target lesions plus the sum of the short axis of all the target lymph nodes at current evaluation) taking as reference the BSD (see Section 11.4.1).
 - O Progression (PD): At least one of the following must be true:
 - At least one new malignant lesion, which also includes any lymph node that was normal at baseline (< 1.0 cm short axis) and increased to ≥ 1.0 cm short axis during follow-up.
 - At least a 20% increase in PBSD (sum of the longest diameter for all target lesions plus the sum of the short axis of all the target lymph nodes at current evaluation) taking as reference the MSD (Section 11.4.1). In addition, the PBSD must also demonstrate an absolute increase of at least 0.5 cm from the MSD.
 - o Stable Disease (SD): Neither sufficient shrinkage to qualify for PR, nor sufficient increase to qualify for PD taking as reference the MSD.
- Evaluation of Non-Target Lesions & Non-target Lymph Nodes
 - o Complete Response (CR): All of the following must be true:
 - Disappearance of all non-target lesions.
 - Each non-target lymph node must have a reduction in short axis to <1.0 cm.

- o Non-CR/Non-PD: Persistence of one or more non-target lesions or non-target lymph nodes
- o Progression (PD): At least one of the following must be true:
 - At least one new malignant lesion, which also includes any lymph node that was normal at baseline (< 1.0 cm short axis) and increased to ≥ 1.0 cm short axis during follow-up.

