Analysis plan for both cohorts: PFS will be compared between treatment arms using the stratified log rank test at one-sided level 0.023. The stratification factors listed in Section 4.6, as collected on the OPEN Enrollment Form, will be used for the analysis. The HR for PFS will be estimated using a stratified Cox proportional hazards model, and the 95% CI for the HR will be provided. Results from an unstratified analysis will also be provided. Kaplan-Meier methodology will be used to estimate the median PFS for each treatment arm, and Kaplan-Meier curves will be produced. Brookmeyer Crowley methodology will be used to construct the 95% CI for the median PFS for each treatment arm [39].

Sensitivity analysis plan for both cohorts:

- The PFS according to investigator assessment will be used as the endpoint for a sensitivity analysis.
- For patients with a PFS event related to the results of a scan performed prior to the time of scheduled restaging, the PFS event will be dated on the date of the next scheduled radiology restaging assessment.

Carcinoid Tumor Cohort – Pre-planned Subgroup Analysis

In the carcinoid tumor cohort, we will perform the subgroup analysis by the subgroups specific below to evaluate whether the treatment effect is consistent across different subgroups. Interaction p-value (interaction between treatment arms and specific subgroups) will be used to determine whether the treatment effect is consistent. A p-value of < 0.1 will indicate that there is a differential treatment effect across different subgroups.

The pre-planned subgroups are:

- Prior Anti-VEGF Therapy: Yes vs. No
- Prior Targeted Radionucleotide Therapy (PRRT): Yes vs. No

[‡] Proportions are based on 10,000 replicates in the simulation study.

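### Section 11.4 does not say that the progression reference (MSD) covers all earlier evaluations; read literally, the target-sum criterion for PD compares only with baseline

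*Combined protocol and SAP*

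**What the plan says.** Section 11.4.1 defines a baseline sum (BSD) and a post-baseline sum. The latter "will be calculated and reported as the post-baseline sum of dimensions (PBSD"), with no visit index. It then defines the reference: "The minimum sum of the dimensions (MSD) is the minimum of the BSD and the PBSD".

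Section 11.4.3 uses that reference for progression. Target-sum PD needs "At least a 20% increase in PBSD", where the PBSD is spelled out as the sum of target lesions and "target lymph nodes at current evaluation) taking as reference the MSD". It also requires that "the PBSD must also demonstrate an absolute increase of at least 0.5 cm from the MSD". Stable disease uses the MSD as well, while partial response is judged against the BSD. PD can also be reached through a new malignant lesion or unequivocal progression of non-target disease (11.4.3, 11.4.4).

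Under 7.2.2, a local determination of PD on blinded therapy sets off the real-time central read. Under 7.2.3, scans read locally as CR, PR or SD go to batched review, and "Results of the batched centralized image reviews will not be reported back to the site PI". Section 13.5.1 adds: "The PFS according to investigator assessment will be used as the endpoint for a sensitivity analysis". Sections 7.2.2, 11.0 and 13.3.1 all name RECIST 1.1 as the governing criteria.

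**The concern.** A separately defined minimum sum serves a purpose only if it can fall below baseline and stay there as the yardstick for later visits. If the PBSD in 11.4.1 means what 11.4.3 says it means, the MSD never does this. The smallest sum reached on study drops out of the rule, and regrowth after shrinkage is measured from baseline.

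Only tumours that shrink are affected. A site applying the literal formula would record stable disease at a visit where another site, using a running minimum, would record PD. The first patient's scan would not trigger the real-time read and would go to a batch whose result is not returned. If one arm shrinks more tumours than the other, later local PD calls would fall mainly in that arm and would favour it in the investigator-PFS sensitivity analysis. Section 1.2.2 reports phase II response rates of 15% with cabozantinib in both tumour types. Patients whose tumours shrink too little to count as responders would be affected too.

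**Working it through.** The plan states no figure for this point, so there is nothing to reproduce. The check is to put the definitions into the PD rule.

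**Inputs.** B = BSD; S = sum at the current visit; N = smallest of B and all sums recorded before the current visit. The PD thresholds are 20% and 0.5 cm over the MSD (11.4.3). The MSD is as defined in 11.4.1.

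**Literal reading: MSD = min(B, S).**
- If S ≤ B, then MSD = S. The increase is S − S = 0, so the sum criterion cannot be met.
- If S > B, then MSD = B. PD needs S ≥ max(1.2B, B + 0.5).
- The two conditions meet where 0.2B = 0.5, so B = 2.5 cm. From there upward the threshold is exactly 20% above baseline. Below it the 0.5 cm condition governs: 2.5 cm for B = 2 cm (25% above baseline) and 1.5 cm for B = 1 cm (50% above).

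**Running-minimum reading: MSD = N.** PD needs S ≥ max(1.2N, N + 0.5).

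**One patient, both readings.** Baseline 10.0 cm, then 7.0 cm, then 8.6 cm.
- Running minimum: 8.6/7.0 = 1.229, or +23%; 8.6 − 7.0 = 1.6 cm. Both thresholds are met: PD.
- Literal: MSD = min(10.0, 8.6) = 8.6; the increase is 0. Not PD by the sum criterion.

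**First sum that counts as PD:**

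| BSD (cm) | Smallest sum (cm) | Literal (cm) | Regrowth, literal | Running minimum (cm) | Regrowth, running minimum |
|---|---|---|---|---|---|
| 10 | 10 (no shrinkage) | 12.0 | 20% | 12.0 | 20% |
| 10 | 9 | 12.0 | 33% | 10.8 | 20% |
| 10 | 8 | 12.0 | 50% | 9.6 | 20% |
| 10 | 7 | 12.0 | 71% | 8.4 | 20% |
| 10 | 5 | 12.0 | 140% | 6.0 | 20% |
| 2 | 1.4 | 2.5 | 79% | 1.9 | 36% |

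For a BSD of at least 2.5 cm and a minimum equal to fraction f of baseline, literal regrowth is 1.2/f − 1: 33% at f = 0.9, 50% at 0.8 and 71% at 0.7. The 20% comparison holds while the smallest sum is itself at least 2.5 cm; below that, 0.5 cm governs, as in the last row. Without shrinkage the two readings agree.

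**The case against.** The strongest reply is that the literal reading is not the natural one. Section 11.4.1 gives the PBSD no visit index, and the word current appears only in 11.4.3. Targets are re-measured every 12 weeks, so there are many post-baseline sums. A term called a minimum sum, kept separate from the BSD and used for PD and SD but not for PR, makes sense only as a running minimum. On that reading the discrepancy vanishes. This stands as evidence of intent. It does not remove the defect: the PBSD is written in the singular, 11.4.3 describes it twice (under PR and PD) as the present sum, and nothing in 11.4 says the minimum runs over all visits. Section 11.5 refers to Section 13 for analysis variables, and Section 13 defines no reference sum.

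The second reply is that RECIST 1.1 governs. A reader might infer from the literal formula that primary PFS is biased. The documents do not support that: 13.3.1 ties the primary endpoint to RECIST 1.1 by retrospective central review, 7.2.2 ties the real-time readers to it, and nothing says central readers compute the MSD from 11.4.1. Section 11.0 covers local reads in the same way. Even so, Section 11.4 is where the criteria are written out for sites, and it holds the only definition of the progression reference in the documents. Section 7.2.3 requires the batch reader to assess only the two time points in each 6-month period and leaves earlier scans optional, so nothing written requires the minimum to be carried across periods.

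The third reply is that PD has other routes. That stands: only the sum criterion is affected.

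**Conclusion.** The wording is ambiguous, and its literal form gives a baseline-only sum criterion. Two readers following the same text can make opposite PD calls on identical measurements after shrinkage. Under the literal form, the regrowth needed is 33%, 50% or 71% from a minimum of 90%, 80% or 70% of baseline (BSD at least 2.5 cm), instead of 20%.

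The exposure is local PD: the trigger for the real-time read and the input to the investigator-PFS sensitivity analysis. The direction is conditional. If sites apply the literal formula, any bias favours the arm with more shrinkage. The documents do not show how many sites would do so.

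Three stronger inferences are not supported. Section 11.4 does not settle on a baseline-only rule. An effect on primary PFS is not shown. The regrowth percentages also cannot be turned into months of delay: that would mean treating the assumed 5-month placebo median PFS of the pancreatic cohort as a tumour growth rate, although PFS also counts deaths, new lesions and non-target progression. No sample size, event count, alpha or power figure depends on this point.

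**What to change.** Replace the MSD sentence in 11.4.1 with: *The MSD is the smallest of the BSD and all PBSDs recorded before the current evaluation.* Tell sites and IROC readers to carry that value forward from visit to visit and across the 6-month review periods.

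Add a programmed check that recomputes the sum criterion from the recorded target sums. Use it to query discordant local calls, or report it as a supplementary analysis. It should not overwrite local PD, because the sensitivity analysis in 13.5.1 is meant to use the investigator's own assessment.

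The cost is one sentence in an amendment, a short notice to sites and readers, and a check on sums that 11.4.1 already requires to be reported.

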11.4.2 Non-Target Lesions & Non-Target Lymph Nodes

Non-measurable sites of disease are classified as non-target lesions or non-target lymph nodes and should also be recorded at baseline. These lesions and lymph nodes should be followed in accord with Section 11.4.3.

11.4.3 Response Criteria

All target lesions and target lymph nodes followed by CT/MRI/Chest X-ray must be measured on re-evaluation at evaluation times specified in Section 11.1. Specifically, a change in objective status to either a PR or CR cannot be done without re-measuring target lesions and target lymph nodes.

Note: Non-target lesions and non-target lymph nodes should be evaluated at each assessment, especially in the case of first response or confirmation of response. In selected circumstances, certain non-target organs may be evaluated less frequently. For example, bone scans may need to be repeated only when complete response is identified in target disease or when progression in bone is suspected.

- Evaluation of Target Lesions
 - o Complete Response (CR): All of the following must be true:
 - Disappearance of all target lesions.
 - Each target lymph node must have reduction in short axis to < 1.0 cm.
 - Partial Response (PR): At least a 30% decrease in PBSD (sum of the longest diameter for all target lesions plus the sum of the short axis of all the target lymph nodes at current evaluation) taking as reference the BSD (see Section 11.4.1).
 - O Progression (PD): At least one of the following must be true:
 - At least one new malignant lesion, which also includes any lymph node that was normal at baseline (< 1.0 cm short axis) and increased to ≥ 1.0 cm short axis during follow-up.
 - At least a 20% increase in PBSD (sum of the longest diameter for all target lesions plus the sum of the short axis of all the target lymph nodes at current evaluation) taking as reference the MSD (Section 11.4.1). In addition, the PBSD must also demonstrate an absolute increase of at least 0.5 cm from the MSD.
 - o Stable Disease (SD): Neither sufficient shrinkage to qualify for PR, nor sufficient increase to qualify for PD taking as reference the MSD.
- Evaluation of Non-Target Lesions & Non-target Lymph Nodes
 - o Complete Response (CR): All of the following must be true:
 - Disappearance of all non-target lesions.
 - Each non-target lymph node must have a reduction in short axis to <1.0 cm.

- o Non-CR/Non-PD: Persistence of one or more non-target lesions or non-target lymph nodes
- o Progression (PD): At least one of the following must be true:
 - At least one new malignant lesion, which also includes any lymph node that was normal at baseline (< 1.0 cm short axis) and increased to ≥ 1.0 cm short axis during follow-up.
 - Unequivocal progression of existing non-target lesions and non-target lymph nodes. (NOTE: Unequivocal progression should not normally trump target lesion and target lymph node status. It must be representative of overall disease status change.)

